10.3. Vital Sign, Weight, and Waist Circumference Measurements

The endpoints for vital sign parameters, weight, and waist circumference include:

- Observed value and change from baseline over time in vital sign parameters including temperature, pulse, and blood pressure
- Shifts from baseline to post-baseline time points and to the worst post-baseline value in terms of normal/abnormal in pulse and blood pressure (normal ranges are defined as: 60-100 beats/minute for pulse, 90-140 mmHg for systolic blood pressure, and 60-90 mmHg for diastolic blood pressure)
- Observed value, change and percent change from baseline over time in weight and waist circumference

Summary statistics (N, Mean, STDEV, Median, Minimum, and Maximum) of observed values, changes from baseline, and percent change from baseline (applicable for weight and waist circumference) will be provided over time. Frequency summaries (shift tables) of shifts from baseline to post-baseline time points and to the worst post-baseline value in terms of normal/abnormal will be provided for pulse and blood pressure.

Frequency summaries of percent change in weight from baseline to the end of the study phase/period will be provided by baseline BMI category (<18.5, 18.5 to < 25, 25 to < 30, \geq 30 kg/m²) and by baseline weight category (< 70, \geq 70 to < 85, \geq 85 to < 100, and \geq 100 kg). The categories of weight change (kg) and percent change (%) are < -20, \geq -20 to < -10, \geq -10 to < -5, \geq -5 to < 0, 0, > 0 to \leq 5, > 5 to \leq 10, > 10 to \leq 20, and > 20.

A subject data listing of all vital sign parameters, weight, and waist circumference data with abnormal flags where applicable and study phase/period flags will be provided.

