	Clinically significant changes in body weight, waist circumference, vital signs, and/or laboratory findings	Frequency of clinically significant changes in body weight, waist circumference, vital signs, and/or laboratory findings.	During double-blinded treatment and throughout the duration of the apremilast treatment
Exploratory			
	Static Physician Global Assessment (sPGA) of Visible locations	Proportion of subjects who achieve sPGA score of 0 or 1 (among subjects randomized with moderate to severe psoriasis in visible areas, defined as sPGA ≥ 3 , which include the dorsal hand, face, neck, or hairline)	Weeks 16, 32, 52
	Scalp Physician Global Assessment (ScPGA)	Proportion of subjects who achieve ScPGA score of 0 or 1 (among subjects randomized with moderate to severe scalp psoriasis, ScPGA ≥ 3)	Weeks 16, 32, 52
	Nail Psoriasis Severity Index (NAPSI)	Proportion of subjects who achieve NAPSI score of 0 in the target fingernail (among subjects randomized with presence of nail psoriasis, defined as onycholysis and onychodystrophy in at least 2 fingernails)	Weeks 16, 32, 52

Table 2: Study Endpoints (Continued)

Endpoint	Name	Description	Timeframe
	Modified Static Physician Global Assessment-Genitalia (sPGA-G)	Proportion of subjects who achieve modified sPGA-G score of 0 or 1 (among subjects randomized with moderate to severe genital psoriasis, modified sPGA-G ≥ 3)	Weeks 16, 32, 52
	Palmoplantar Psoriasis Physician Global Assessment (PPPGA)	Proportion of subjects who achieve PPPGA score of 0 or 1 (among subjects randomized with moderate to severe palmoplantar psoriasis, PPPGA ≥ 3)	Weeks 16, 32, 52

Approved

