6.5.5. Severe Diarrhea, Nausea and Vomiting

There have been post-marketing reports of severe diarrhea, nausea, and vomiting associated with the use of apremilast. Most events occurred within the first few weeks of treatment. In some cases, patients were hospitalized. Patients 65 years of age or older and patients taking medications that can lead to volume depletion or hypotension may be at a higher risk of complications. Subjects should be monitored for severe diarrhea, nausea and vomiting. If patients develop severe diarrhoea, nausea, or vomiting, discontinuation of treatment may be necessary (see Section 11).

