9.7. Safety Analysis

The safety analyses will be performed using the safety population as defined in Section 9.2, defined as all subjects who are randomized and receive at least one dose of investigational product. Safety will be assessed by clinical review of all relevant parameters including treatment-emergent adverse events (TEAEs), laboratory tests, and vital signs; no inferential testing for statistical significance will be performed. Data from safety assessments will be summarized descriptively for the Placebo-controlled Phase (Weeks 0 to 16) and the Apremilast Exposure Period when subjects receive apremilast treatment. For safety analyses in the Placebo-controlled Phase, baseline will be relative to the first dose date following randomization at Week 0. For safety analyses in Apremilast Exposure Period, baseline will be relative to the first apremilast dose date at Week 0 for subjects initially randomized to apremilast or Week 16 for subjects initially randomized to placebo and switched to apremilast in the Apremilast Extension Phase (Weeks 16-52).

Adverse events will be classified using the Medical Dictionary for Regulatory Activities (MedDRA) classification system. Adverse events will be tabulated by study phase (Double-blind Placebo-controlled Phase or apremilast Exposure Phase). All treatment-emergent adverse events (AEs) will be summarized by system organ class, preferred term, severity, and relationship to IP. Adverse events leading to death or to discontinuation from treatment and serious AEs will also be summarized and listed separately.

Laboratory data will be summarized using shift tables showing the number of subjects with low, normal, and high values based on the normal ranges, pretreatment versus post-treatment.

Vital sign measurements, including weight, will be summarized by visit descriptively (count, mean, median, standard deviation, and range). In addition, shift tables showing the number of subjects with values below, within and above the normal reference ranges pretreatment versus post-treatment will be provided.

The changes and percent changes in body weight will be summarized by visit. In addition, the changes by baseline body mass index (BMI; (< 18.5, 18.5 to < 25, 25 to < 30, 30 to < 35, 35 to < 40, \geq 40 kg/m²) will be explored.

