Descriptive statistics will be provided for vital signs, weight, waist circumference, laboratory values (continuous measurements) by treatment and visit, including the end of phase/period visits. The baseline value, value at the time point, and change from baseline (also percent change from baseline if applicable) will be summarized for subjects who have values at baseline and at the time point.

Shift tables, that is, tables summarizing the baseline categories (normal, abnormal) versus the category at the end of the respective periods or versus the worst post-baseline category, include subjects who have values at baseline and at least one post-baseline value. Similarly, in frequency summaries of shifts from baseline at scheduled study weeks per protocol, only subjects who have values at baseline and at the corresponding time point will be included.

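### SAP 10.3 states pulse and blood-pressure shifts as normal/abnormal, where Protocol 9.7 asks for low, normal and high; the change is undeclared and 'worst' has no direction

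*SAP*

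**What the plan says.** For vital signs, Protocol 9.7 (Safety Analysis) states that "shift tables showing the number of subjects with values below, within and above the normal reference ranges pretreatment versus post-treatment will be provided". That is a three-level table.

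SAP 10.3 describes the corresponding output as "Shifts from baseline to post-baseline time points and to the worst post-baseline value in terms of normal/abnormal in pulse and blood pressure". It gives two-sided ranges, "60-100 beats/minute for pulse, 90-140 mmHg for systolic blood pressure, and 60-90 mmHg for diastolic blood pressure", and its later sentence on the frequency summaries again names only normal and abnormal. The general definition in SAP 10 is "tables summarizing the baseline categories (normal, abnormal) versus the category at the end of the respective periods or versus the worst post-baseline category".

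SAP 10.2 is more explicit for laboratory tests. It adds low or high in brackets after normal/abnormal and names High, Low and Normal as the categories. SAP Section 13 declares two departures from the protocol, the multiplicity strategy and the per-protocol population, and nothing on safety tables.

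For weight, Protocol 9.7 asks for change and percent change by visit, and for changes by baseline BMI to be explored. SAP 10.3 gives descriptive statistics over time and adds: "Frequency summaries of percent change in weight from baseline to the end of the study phase/period will be provided by baseline BMI category" (and by baseline weight category).

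Protocol Table 2 lists as a secondary endpoint "Frequency of clinically significant changes in body weight, waist circumference, vital signs, and/or laboratory findings", over double-blind treatment and over the whole of apremilast treatment.

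**The concern.** With a two-sided range, abnormal covers two opposite findings. A table that merges them cannot say how many subjects had low blood pressure or a low pulse, and it hides any movement from one side of the range to the other.

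For pulse and blood pressure the shift tables are the only output in SAP 10.3 that counts subjects. The laboratory marked-abnormality criteria in SAP 15.4, which lead to an incidence and an exposure-adjusted rate, contain no vital signs. If the shift tables lose direction, no other table in that section restores it, although the endpoint in Protocol Table 2 is a frequency.

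The weight table raises a smaller, related question. It takes one value per subject, at the end of the phase or period, whereas the pulse, blood-pressure and laboratory shift tables also use the worst value.

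**Working it through.** The plan states no figure on this point, so there is nothing to reproduce. The check maps one table layout onto the other and counts the visits that reach the weight table.

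**1. Three levels against two.** Inputs: the three levels in Protocol 9.7, the two in SAP 10.3, and the SAP's own ranges. A three-level shift table has 3 × 3 = 9 cells and a two-level table has 2 × 2 = 4. The nine cells fall into the four as follows.

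| SAP cell (baseline to post-baseline) | Three-level cells merged into it | Number |
|---|---|---|
| normal to normal | normal–normal | 1 |
| normal to abnormal | normal–low, normal–high | 2 |
| abnormal to normal | low–normal, high–normal | 2 |
| abnormal to abnormal | low–low, low–high, high–low, high–high | 4 |

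The total is 1 + 2 + 2 + 4 = 9.

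**2. Examples with the SAP's systolic range of 90 to 140 mmHg.**
- 120 to 85 is normal to low; the SAP cell is normal to abnormal.
- 120 to 150 is normal to high; the SAP cell is again normal to abnormal, so opposite changes share a cell.
- 150 to 85 is high to low; the SAP cell is abnormal to abnormal, which reads as no shift.

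**3. Direction of the worst value.** Take a subject with post-baseline systolic values of 85 and 150. With two categories the worst category is abnormal whichever value is chosen, but the table does not say on which side. With three categories the same subject could be placed under low or under high, and the SAP gives no rule. Now take 95 and 150. If worst means the lowest value the subject is normal; if it means the highest, abnormal. Moving to three categories therefore also requires a definition of worst.

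**4. Weight.** Input: the Table of Events in Protocol Section 5, with post-baseline weights at Weeks 2, 4, 16, 20, 32, 44 and 52. For a subject who completes, the frequency table uses:
- placebo-controlled phase (Weeks 2, 4, 16): 1 of 3 scheduled weights;
- exposure period, on apremilast from Week 0: 1 of 7;
- exposure period, switched at Week 16 (Weeks 20, 32, 44, 52): 1 of 4.

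As an assumed course, take percent changes of -6, -11 and -1 at Weeks 2, 4 and 16. The planned table files this subject in the band from -5 to below 0. The largest loss, -11, belongs in the band from -20 to below -10.

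**The case against.** The strongest reply is that normal/abnormal is shorthand. SAP 10.2 defines three laboratory categories, yet its own sentence on the shift-table output says only normal/abnormal. The SAP 10 definition covers those three-level laboratory tables too, so it does not prove a collapse. Two-sided ranges in SAP 10.3 and the silence of Section 13 would fit an intention to follow the protocol. This stands as a possible reading. It does not settle the matter, because SAP 10.3 has neither the bracketed low or high nor the named categories of 10.2, and a programmer following it would build a two-by-two table.

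A reader might infer that low blood pressure goes uncounted. That is too strong. A subject who was normal at baseline and falls below range is counted as abnormal; what is missing is a separate count of low values. Minima and maxima over time and a subject listing with abnormal flags are also planned, though these show values and not numbers of subjects.

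A reader might also take Protocol 6.5.5 as naming hypotension as an effect of apremilast. It says that "patients taking medications that can lead to volume depletion or hypotension may be at a higher risk of complications". That concerns co-medication and complications of severe gastrointestinal events, and the point here does not rest on it.

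On weight, the objection largely succeeds. Protocol 9.7 asks for by-visit changes and SAP 10.3 supplies them; no section requires a worst-value table. In the placebo-controlled phase an early leaver's end date is the discontinuation visit (SAP 5.2.1), so loss present at stopping is captured. The Table of Events directs adverse-event review to clinically significant unexplained weight loss, which is then tabulated by preferred term if reported. What remains is that the frequency table misses transient loss in subjects who stay on treatment.

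**Conclusion.** The mismatch holds: the protocol asks for three levels, the SAP states two for pulse and blood pressure, and Section 13 does not declare the difference. On the literal reading, nine cells become four, low values are not counted separately, a high-to-low change shows as no shift, and the worst value has no direction. If the SAP authors meant shorthand, the consequence disappears but the wording still needs correcting, and the direction of worst still needs a rule.

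The size is modest. These are descriptive tables, and the primary endpoint, sample size and data collection are unaffected. A reader might infer that a difference between arms in low blood pressure would be hidden. The documents give no rates of low or high readings in either arm, and Protocol 9.7 excludes inferential safety testing, so no size can be put on that.

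The weight table is not an error and not a breach of the protocol. A table on the largest loss would be a cheap improvement that serves the Table 2 endpoint.

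**What to change.** In SAP 10.3, replace normal/abnormal with low/normal/high for pulse, systolic and diastolic pressure, using the ranges already given, in line with Protocol 9.7 and SAP 10.2. Align the general definition of shift tables in SAP 10.

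Replace the single shift to the worst value with two: one to the lowest and one to the highest post-baseline value. This goes beyond Protocol 9.7 but is needed to define worst for a two-sided range. If two categories are in fact intended, declare that in Section 13 with a reason.

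Optionally, add a weight frequency table on the largest percent loss at any post-baseline visit in the phase or period, with the existing cut-points, beside the end-of-phase table.

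The cost is a wording change in the SAP and a few more table rows from data already collected, with no burden on subjects or sites.

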11. QUALITY OF LIFE ANALYSIS

The Quality of life endpoints, including DLQI (the primary endpoint), EQ-5D (secondary endpoint and WPSI:PSO (secondary endpoint) have been addressed in section 9.

12. INTERIM ANALYSIS

No interim analysis will be conducted. No DMC is planned for this study either.

For publication purpose, analyses on the data up to the primary timepoint of Week 16 are planned based on a Week 16 data transfer after all subjects have completed the Week 16 Visit (or discontinued from the study). However, unblinded data will only be made available to selected Sponsor and Contract Research Organization (CRO) team members involved with Week 16 data analysis and publication preparations. All other Sponsor, site, and CRO personnel directly involved with the conduct of the study, will remain blinded to treatment assignments until the final database lock at the final study completion. After all subjects have completed the Observational Follow-up Phase following the Week 52/discontinuation visit in the Apremilast Extension Phase (Weeks 16 to 52), the final database will be locked and transferred for all analyses planned in this SAP, based on which, a Clinical Study Report will be generated.

**13. CHANGES TO THE STATISTICAL ANALYSES SECTION OF
THE PROTOCOL**

In order to control the overall type I error rate, the multiplicity adjustment is made to the primary endpoint and some secondary endpoints by following the hierarchical rank for testing in Section 9.2. This is deviated from Section of 9.6.5 in the protocol, where no multiplicity adjustment is planned.

Per-protocol (PP) population includes all subjects who are in the ITT population, who receive at least one dose of IP, have both baseline and at least one post-treatment DLQI evaluation, and have no major protocol deviations which may affect analyses in the Placebo-controlled Phase. This definition is deviated from Section 5.3.2 in the protocol.

15. APPENDICES

15.1. Handling of Dates

Dates will be stored as numeric variables in the SAS analysis files and reported in DDMMYY format (i.e., the Date9. datetime format in SAS).

15.1.1. Calculation Using Dates

Calculations using dates (e.g., subject's age or relative day after the first dose of study drug) will adhere to the following conventions:

- Study days after the start day of study drug will be calculated as the difference between the date of interest and the first date of dosing of study drug plus 1 day. The generalized calculation algorithm for relative day is the following:

- If TARGET DATE \geq DSTART then STUDY DAY = (TARGET DATE – DSTART) + 1;
 - Else use STUDY DAY = TARGET DATE – DSTART.

Depending on the study day definition, DSTART can be Day 1 for core baseline or the Day 1 for Apremilast treatment baseline. Negative study days are reflective of observations obtained before the corresponding baseline. Note: Partial dates for the first study drug are not imputed in general. All effort should be made to avoid incomplete study drug start dates.

- Age (in years) at the time of informed consent is collected.
 - When age in years is not available, age in days is calculated as (informed consent date – July 15 on the year of birth) + 1. Then age in years will be transformed to years by dividing age in days by 365.25 days, then truncating
 - If year of birth is also missing, set age missing
- Intervals that are presented in weeks will be transformed from days to weeks by using (without truncation) the following conversion formula:

$$\text{WEEKS} = \text{DAYS} / 7$$

- Intervals that are presented in months will be transformed from days to months by using (without truncation) the following conversion formula:

$$\text{MONTHS} = \text{DAYS} / 30.4167$$

15.2. Date Imputation Guideline

15.2.1. Adverse Events

Partially missing AE start dates will be imputed in the ADaM dataset for AEs, but partially missing AE end dates will not be imputed. If the AE end date is complete with no missing year, month, or day, and the partially missing start date imputed by the rules below is after the AE end date, then the start date will be imputed by the AE end date.

Subjects who were treated with Apremilast at Week 0/Visit 2

The principle of the imputation rules for subjects who were treated with Apremilast initially is to treat the AE as treatment-emergent, i.e., occurring on or after the date of the first dose of Apremilast, if possible.

Let an AE start date be represented as " $D_{Event}/M_{Event}/Y_{Event}$ ", and the date of the first dose of Apremilast as " $D_{APR}/M_{APR}/Y_{APR}$ ". The following table gives the imputation rules for partially missing AE start dates for subjects who were treated with Apremilast initially at Week 0/Visit 2.

Table 6 Imputation Rules for Partially Missing AE Start Dates for Subjects Who Were Treated with Apremilast Initially

Scenario	Condition	Imputation Rule
Partially missing date includes year only (both month and day are missing)		
1	$Y_{Event} < Y_{APR}$	12/31/ Y_{Event}
2	Otherwise, i.e., $Y_{APR} \leq Y_{Event}$	Max (date of first dose of Apremilast, 1/1/ Y_{Event})
Partially missing date includes both year and month (only day is missing)		
1	$Y_{Event} < Y_{APR}$, or ($Y_{Event} = Y_{APR}$ and $M_{Event} < M_{APR}$)	Last date of M_{Event}/Y_{Event}
2	Otherwise, i.e., $Y_{APR} < Y_{Event}$, or ($Y_{APR} = Y_{Event}$ and $M_{APR} \leq M_{Event}$)	Max (date of first dose of Apremilast, 1/ M_{Event}/Y_{Event})

Subjects who were treated with placebo at Week 0/Visit 2

The principle of the imputation rules for subjects who were treated with placebo initially and started Apremilast treatment at Week 16 is to consider the AE starting on or after the date of the first dose of Apremilast, if possible; if the partially missing start date suggests that it is prior to the date of the first dose of Apremilast, the AE will be considered starting on or after the date of the first dose of placebo, if possible.

The following are 4 scenarios considered in the imputation rules:

1. The partially missing AE start date suggests the date is prior to the date of the first dose of placebo: impute it by the latest possible date (determined by the non-missing field of the date);

Apremilast

Statistical Analysis Plan. Protocol CC-10004-PSOR-020

Amgen INC.

2. The partially missing AE start date suggests the date is after the date of the first dose of Apremilast following Week 16: impute it by the earliest possible date (determined by the non-missing field of the date);
3. The partially missing AE start date is in the same year (if both month and day are missing), or the same year/month (if only day is missing) of the first dose of Apremilast following Week 16: impute it by the date of the first dose of Apremilast;
4. The partially missing AE start date suggests the date is no earlier than the date of the first dose of placebo but prior to the date of the first dose of Apremilast following Week 16: impute it by the date of the first dose of placebo, or the earliest possible date (determined by the non-missing field of the date), whichever occurs later.

Let an AE start date be represented as " $D_{Event}/M_{Event}/Y_{Event}$ ", the date of the first dose of placebo as " $D_{PBO}/M_{PBO}/Y_{PBO}$ ", and the date of the first dose of Apremilast following Week 16 as " $D_{APR}/M_{APR}/Y_{APR}$ ". The following table gives the imputation rules for partially missing AE start dates.

Table 7 Imputation Rules for Partially Missing AE Start Dates for Subjects Who Were Treated with Placebo Initially

Scenario	Condition	Imputation Rule
Partially missing date includes year only (both month and day are missing)		
1	$Y_{Event} < Y_{PBO}$	$12/31/Y_{Event}$
2	$Y_{Event} > Y_{APR}$	$1/1/Y_{Event}$
3	$Y_{Event} = Y_{APR}$	Date of first dose of Apremilast following Week 16
4	Otherwise, i.e., $Y_{PBO} \leq Y_{Event} < Y_{APR}$	Max (date of first dose of PBO, $1/1/Y_{Event}$)
Partially missing date includes both year and month (only day is missing)		
1	$Y_{Event} < Y_{PBO}$, or $(Y_{Event} = Y_{PBO} \text{ and } M_{Event} < M_{PBO})$	Last date of M_{Event}/Y_{Event}
2	$Y_{Event} > Y_{APR}$, or $(Y_{Event} = Y_{APR} \text{ and } M_{Event} > M_{APR})$	$1/M_{Event}/Y_{Event}$
3	$Y_{Event} = Y_{APR}$ and $M_{Event} = M_{APR}$	Date of first dose of Apremilast following Week 16
4	Otherwise, i.e., $Y_{PBO} < Y_{Event} < Y_{APR}$, or $(Y_{PBO} = Y_{Event} < Y_{APR} \text{ and } M_{PBO} \leq M_{Event})$, or $(Y_{PBO} = Y_{Event} = Y_{APR} \text{ and } M_{PBO} \leq M_{Event} < M_{APR})$, or $(Y_{PBO} < Y_{Event} = Y_{APR} \text{ and } M_{Event} < M_{APR})$	Max (date of first dose of placebo, $1/M_{Event}/Y_{Event}$)

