5.2.1. Placebo-controlled Phase – Weeks 0 to16

The Placebo-controlled phase is per protocol specification. All the efficacy and safety analyses for the primary time point at Week 16 are based on placebo-controlled phase, including data collected from Day 1 for the core baseline (defined in Section 5.4). The end date is defined as following:

- (1) One day prior to the first dose date of Apremilast dispensed at Week 16/Visit 5 for patients who are entering the Apremilast Extension Phase;
- (2) the day of the discontinuation visit if the subject discontinued prior to or at Week 16/Visit 5;

Apremilast

Statistical Analysis Plan. Protocol CC-10004-PSOR-020

Amgen INC.

- (3) the last known study day if the subject is lost to follow-up prior to Week 16/Visit 5.

All by-treatment tabulations based on the data from Placebo-controlled Phase are grouped by Apremilast 30 mg BID vs. placebo.

5.2.2. Apremilast Extension Phase – Weeks 16 to 52

The Apremilast Extension Phase is per protocol specification. Quality of life and efficacy endpoints, patient disposition, protocol deviation/violation, and study treatment compliance are summarized based on data from this study phase.

The Apremilast Extension Phase starts on the day that the first dose of treatment is dispensed for the phase at Week 16/visit 5 and the end date is defined as the following:

- (1) the day of Week 52/Visit 9 for patients who complete the study on treatment;
- (2) the day of the discontinuation visit if the subject discontinued prior to or at Week 52/Visit 9;
- (3) the last known study day if the subject is lost to follow-up prior to Week 52/Visit 9.

All by-treatment tabulations are grouped by Apremilast 30 mg BID arm vs. placebo arm, i.e., the original treatment during the placebo-controlled phase.

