10. SAFETY ANALYSIS

Safety will be assessed via descriptive statistics and point estimates on observed data.

All safety analyses described in this section will be performed for both the Placebo-controlled Phase and the Apremilast Exposure Period. The safety analyses for the Placebo-controlled Phase will be based on the safety population and presented by treatment arm (placebo, and Apremilast 30 mg BID). The safety analyses for the Apremilast Exposure Period will be based on the Apremilast Exposure Population and presented by Apremilast dose group (i.e., Apremilast 30 mg BID) irrespective of the start time of Apremilast exposure (at Week 0 or 16). In addition, selected summaries on AEs for the Observational Follow-up Phase will be listed.

For the analyses of AEs and laboratory marked abnormalities, both subject incidence and exposure-adjusted incidence rate (EAIR) per 100 subject-years for the Placebo-controlled Phase (Weeks 0 to 16) and for the Apremilast Exposure Period will be provided. The point estimates of subject incidence and EAIR are distinguished as following:

- Subject incidence: is defined as the number of subjects with the specific event divided by the number of subjects included in the analysis (i.e., percentage [%] used in a frequency summary). Subjects with multiple occurrences of the specific event in the specific analysis period will be counted only once in the numerator.
- Exposure-adjusted incidence rate (EAIR) per 100 subject-years: The EAIR per 100 subject-years is defined as 100 times the number of subjects with the specific event divided by the total exposure time (in years) among subjects included in the analysis. Subjects with multiple occurrences of the specific event in the specific analysis period will be counted only once in the numerator. The exposure time for a subject without the specific event is the treatment duration (i.e., last dose date-first dose date+1), whereas the exposure time for a subject with the specific event is the treatment duration up to the start date (inclusive) of the first occurrence of the specific event. The total exposure time in years is calculated by dividing the sum of exposure time in days over all subjects included in the analysis by 365.25. The EAIR per 100 subject-years is interpreted as the expected number of subjects with at least one occurrence of the specific event per 100 subject-years of exposure to the IP.

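### Partial AE start dates that share the Week 16 switch month or year are placed inside the placebo-controlled phase for apremilast starters and outside it for placebo starters

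*SAP*

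**What the plan says.** SAP 15.2.1 has two sets of rules for partially missing AE start dates, chosen by initial treatment.

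- **Apremilast starters (Table 6).** The aim "is to treat the AE as treatment-emergent, i.e., occurring on or after the date of the first dose of Apremilast, if possible". Unless the date is clearly before first dose, the start becomes the later of the first apremilast dose and the first day of the known month, or 1 January of the known year.
- **Placebo starters (Table 7).** The aim "is to consider the AE starting on or after the date of the first dose of Apremilast, if possible". Scenario 3 covers a partial date in the same year, or the same year and month, "of the first dose of Apremilast following Week 16: impute it by the date of the first dose of Apremilast". Scenario 4, for dates that point to the time before the switch, says "impute it by the date of the first dose of placebo, or the earliest possible date", whichever is later.

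In both arms, a complete AE end date caps the imputed start: if the imputed start falls after the end date, the end date is used instead.

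The phase boundary is in SAP 5.2.1. The Placebo-controlled Phase ends "One day prior to the first dose date of Apremilast dispensed at Week 16/Visit 5 for patients who are entering the Apremilast Extension Phase". SAP 10.1 cuts the treatment-emergent window at the phase end. SAP 10 adds: "All safety analyses described in this section will be performed for both the Placebo-controlled Phase and the Apremilast Exposure Period". SAP 5.2.3 gives the Apremilast Exposure Period a single arm. Safety against placebo at Week 16 is a secondary objective (SAP 3.2).

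**The concern.** A rule that assigns doubtful AEs to apremilast is cautious where there is only an apremilast column. SAP 15.2.1 describes one imputed start date per AE, and that date also decides what enters the two-arm Weeks 0-16 table. There the same caution works in opposite directions: a doubtful date near the switch adds an event to the apremilast column and removes one from the placebo column. Two identical records are classified by arm alone.

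At stake is the only safety table with a randomised comparator. EAIR is touched twice. Under SAP 10, exposure for a subject with the event stops at its start date, so an AE pulled forward on apremilast adds an event and shortens exposure. An AE pushed out on placebo loses the event and keeps full phase exposure. SAP 10 and 13 give no offsetting rule or sensitivity analysis.

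There is also a gap. The placebo rules are written for subjects who started apremilast at Week 16, and scenarios 2 to 4 of Table 7 all need that date. Placebo subjects who leave earlier have no such date.

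**Working it through.** The documents give no figure for this, so there is none to reproduce. The check applies Tables 6 and 7 to identical AEs in both arms.

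**1. One worked case.** First dose 4 March 2019; Week 16 dose 112 days later, 24 June 2019. The phase ends 23 June.

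| Recorded start | Apremilast starter | Placebo starter |
|---|---|---|
| Feb 2019 | 28 Feb, out | 28 Feb, out |
| Mar 2019 | 4 Mar, in | 4 Mar, in |
| May 2019 | 1 May, in | 1 May, in |
| **Jun 2019** | **1 Jun, in** | **24 Jun, out** |
| Jul 2019 | 1 Jul, out | 1 Jul, out |
| **2019 only** | **4 Mar, in** | **24 Jun, out** |

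Only dates sharing the switch month, or the switch year when only the year is known, diverge.

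**2. All start dates.** Assumptions not in the documents: first doses on every day of one calendar year, AE onset uniform over 364 days, equal true rates in both arms, every placebo subject switching on Day 113. The true in-phase share is 112/364 = 0.308. Let r be the in-phase count after imputation divided by the true in-phase count. With no usable AE end date:

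| | r, apremilast | r, placebo | Apremilast extension AEs pulled in | Placebo in-phase AEs pushed out |
|---|---|---|---|---|
| Day missing | 1.132 | 0.868 | 5.9% | 13.2% |
| Year only | 2.470 | 0.155 | 65.3% | 84.5% |

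Hand check for day missing: in a month of n days, the days before the switch sum to n(n-1)/2 over all possible switch days. Over an ordinary year the mean is (7×465 + 4×435 + 378)/365 = 14.7 days, and 14.7/112 = 0.13. Placebo therefore falls to about 0.87. By symmetry about the same number of extension days is pulled in for apremilast, giving about 1.13.

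**3. The end-date cap.** With a complete end date the given number of days after onset, r for placebo becomes:

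| AE duration | Day missing | Year only |
|---|---|---|
| 0 days | 1.000 | 1.000 |
| 7 days | 0.946 | 0.938 |
| 30 days | 0.868 | 0.744 |
| 90 days | 0.868 | 0.297 |

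Apremilast stays at 1.132 and 2.470 throughout. The earliest possible date cannot fall after the end of an on-treatment AE, so the cap never acts on one.

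**4. Effect on total AE counts.** If a share q of AE records is partial, the apremilast:placebo ratio of in-phase counts is [(1-q) + q·r(apremilast)] / [(1-q) + q·r(placebo)]. It would be 1 without the rule. Example, year only, q = 0.10, no end date: (0.90 + 0.247)/(0.90 + 0.0155) = 1.147/0.9155 = 1.253.

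| q | Day missing, no end date | Day missing, 7-day AEs | Year only, no end date | Year only, 7-day AEs |
|---|---|---|---|---|
| 2% | 1.005 | 1.004 | 1.047 | 1.031 |
| 5% | 1.013 | 1.009 | 1.121 | 1.077 |
| 10% | 1.027 | 1.019 | 1.253 | 1.154 |

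The range for q is an assumption.

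**The case against.** The SAP states its principle openly, and the distortion runs against the sponsor's own drug, so it cannot hide an apremilast harm. Safety is descriptive (protocol 9.7, SAP 10) and no decision rule hangs on it. Year-only dates should be rare: investigators record AE start and stop dates (protocol 10.2.4), AEs are reviewed at every visit, and edit checks, source verification and cleaning before the Week 16 transfer all apply. Early leavers weaken the effect. Placebo subjects who never switch have no date to be pushed to, and apremilast subjects who leave early have few later AEs to pull forward. The tables also count a subject once per event, so moving one record often changes nothing.

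Most of this stands as a limit on size. None of it removes the asymmetry. Caution justifies the rule in the single-arm exposure tables; in a two-arm table, raising one column and lowering the other is bias whichever side it favours. The end-date cap repairs only part of the placebo side. Descriptive reporting means that readers compare the columns directly.

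A reader might infer that all undated AEs are shifted. The documents do not support that: 15.2.1 covers partially missing dates only, gives no rule for a wholly missing start date, and treats the arms alike outside the switch month or year. A reader might also take 2.47 against 0.16 as the expected distortion. Those figures apply only to year-only records with no usable end date, with every placebo subject switching.

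**Conclusion.** The point holds in a limited form. For partial AE start dates that share the switch month or year, SAP 15.2.1 classifies identical records by arm, and the Weeks 0-16 safety comparison is biased against apremilast. With 2-10% of AE records partial, the spurious ratio of AE counts is about 1.004-1.03 when only the day is missing and 1.03-1.25 when only the year is known. These ranges rest on the uniform timing, equal true rates and universal switching assumed above. The share of partial dates is not in the documents.

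The effect on subject incidence and EAIR was not computed; for subject incidence it is probably small. The documents do not support a claim that the safety conclusions would change, that any test is affected, or that particular kinds of AE are the ones with vague dates. The missing branch for placebo subjects who never receive apremilast is a separate gap in wording, not further evidence of bias. The direction is certain and the repair is cheap, so the change is worth making.

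**What to change.** In SAP 15.2.1, for the Placebo-controlled Phase tables only, use one rule in both arms: the later of the first double-blind dose and the earliest date that the known fields allow, with the existing end-date cap. Dates clearly before the first double-blind dose stay under scenario 1, which is already the same in both tables. State that the rule also covers placebo subjects who never receive apremilast. Keep Table 7 scenario 3 for the single-arm Apremilast Exposure tables.

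Identical records are then classified identically, so the spurious ratio becomes 1.00. A common upward shift remains: under the assumptions above, both arms read 1.13 times the truth for day-missing records and 2.47 times for year-only records. Bounding the start by the visit interval would reduce this, but should be added only if the eCRF records the visit at which the AE was first reported, which the documents do not say.

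The cost is a second derived date or phase flag and a footnote. Some placebo-arm AEs may appear in both sets of tables, and the phase flag in the SAP 10.1.2 listings must say which date it follows. SAP 2 has the plan signed before the Week 16 data transfer, so the wording belongs there before that point.
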